#### 8. STATISTICS AND DATA ANALYSIS

## 8.1 STATISTICAL PLAN INCLUDING INTERIM ANALYSIS

Sample Size:

#### 1. For equivalence of DVD programme and face-to-face programme.

In a previous HTA study comparing different pharmacotherapy options in asthma (the ELEVATE study, Controlled-Trials.com number, ISRCTN99132811, Price et al, 2011), treatments were deemed to be equivalent if the 95% CI for mean difference between groups in AQLQ was wholly included between -0.3 and +0.3. Our sample size calculation for equivalence therefore uses the same equivalence boundary (i.e. between -0.3 and +0.3). However, we have assumed that the SD of the between group difference in AQLQ will be a conservative 25% smaller (i.e. 0.77) than that reported in our GLAD study (1.03). The justification for this is that the proposed equivalence analysis will compare two breathing training interventions as opposed to a breathing intervention versus usual care in the GLAD study. Since this is an equivalence study, as opposed to a non-inferiority study, a two-tailed 5% significance level was used in the calculations (29). Following published guidelines (30), the equivalence margin was therefore selected to be 'the largest difference that can be judged to be clinically acceptable and should be smaller than differences observed in superiority trials of the active comparator'.

Using Nquery 7.0 (specifically the MTEOU-1 two group t-test of equivalence in means – unequal n's program), the following justification of the sample size is obtained:

Sample sizes of 210 in the DVD breathing retraining group and 105 in the 'face-to-face' physiotherapy group are required to assess treatment equivalence with 90% power using an equivalence boundary for AQLQ of 0.3. This assumes: that the expected between group difference in mean AQLQ is zero; a two tailed 5% significance level; common standard deviation for AQLQ of 0.77 and a lower/upper limit of -0.3/+0.3 for the 95% confidence interval of the between group difference in AQLQ.

In the unlikely event that the between group AQLQ standard deviation is higher than our estimated 0.77, assuming all other parameters stayed the same, we would still have 80% power to declare equivalence between the DVD breathing retraining group and the 'face-to-face' physiotherapy group as long as the between group SD was no higher than 0.89.

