The methodology of this RCT is based on that of the GLAD study, a 2 armed RCT comparing face-to-face physiotherapist breathing instruction with a control of asthma education (16).

We will perform a pragmatic observer blinded 3 arm parallel group randomised controlled trial comparing a breathing retraining programme delivered through a DVD with a 'face-to-face' physiotherapist programme and a 'control' arm receiving usual care for adults with asthma and impaired health status. Three arms are needed to confirm superiority of the DVD over usual care and comparable efficacy to 'face-to-face' physiotherapy. The study is dual powered to show superiority of the breathing retraining DVD over usual care and equivalence with 'face-to-face' physiotherapist instruction. The focus of this research is on the DVD, as this is most likely to be translated into every-day practice. As the face-to-face physiotherapy already has evidence of effectiveness, and our aim is to show comparable effectiveness of the DVD and superiority of the DVD over usual care, we are using a 2:2:1 randomisation plan (DVD: usual care: face-to-face physiotherapy). This will reduce the costs and logistics of the trial, as the face-to-face intervention is associated with the largest use of time and resources. Subjects will be recruited in the setting of UK general practices who are members of the South-West Primary Care Research Network. Broad entry criteria will be used to allow representative patients to participate and so provide the trial with external validity. The RCT is described in detail below. An internal pilot will initially occur in two GP practices. An assessment of the recruitment rate and of the logistics of the trial protocol will

BREATHE Page 16 of 35 Protocol v6 01-08-2014

be made after this internal pilot, and minor protocol adjustments made as appropriate. Provided significant protocol changes are not made, it is planned to include the data from subjects participating in the pilot in the final analysis.

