## 2. For superiority of both the DVD-delivered and the face-to-face programme over 'usual care'

For the superiority sample size calculations, there is no widely acceptable MCID for between group change in AQLQ, although the MCID for within person change in AQLQ is reported to be 0.5 (SD 0.41) (31). Therefore, we approached the superiority sample size calculation in two ways. Firstly, using the published within person MCID of 0.5 and secondly, using estimates from the GLAD study, a between group mean (SD) difference in AQLQ at 6 months of 0.38 (1.03). Using an MID of 0.5

Nquery 7.0 (specifically the MTTOU-1 two group t-test of equal means – unequal n's program) shows that a two group t-test with a 5% one-sided significance level will have 90% power to detect a difference in mean AQLQ of 0.5 or greater, assuming that the common standard deviation is 0.41, when the

BREATHE Page 26 of 35 Protocol v6 01-08-2014

sample sizes are 10 in the face-to-face breathing retraining and 20 in the 'usual care' groups.

Similarly, a two group t-test with a 5% one-sided significance level will have 90% power to detect a difference in mean AQLQ of 0.5 or greater, assuming that the common standard deviation is 0.41, when the sample size is 13 in each of the DVD-delivered and 'usual care' groups.

Using an MID of 0.38

A two group t-test with a 5% one-sided significance level will have 92% power to detect a difference in mean AQLQ of 0.38 or greater, assuming that the common standard deviation is 1.03, when the sample sizes are 105 in the face-to-face breathing retraining and 210 in the 'usual care' groups.

Similarly, a two group t-test with a 5% one-sided significance level will have 90% power to detect a difference in mean AQLQ of 0.38 or greater, assuming that the common standard deviation is 1.03, when the sample size is 130 in each of the DVD-delivered and 'usual care' groups.

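### Equivalence power rests on an SD of 0.77 that lacks a valid justification and sits beside 1.03 for the same arms elsewhere; under the protocol's own 95% CI rule, power is about 80% at 0.77 and 36% at 1.03, against a stated 90%

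*Protocol*

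**What the plan says.** Protocol section 8.1, Sample Size, item 1 (equivalence of DVD and face-to-face) states: "we have assumed that the SD of the between group difference in AQLQ will be a conservative 25% smaller (i.e. 0.77"). The reference value is the 1.03 of the earlier GLAD trial. The reason offered is that "the proposed equivalence analysis will compare two breathing training interventions as opposed to a breathing intervention versus usual care in the GLAD study". The value then enters the calculation as a "common standard deviation for AQLQ of 0.77". With 210 v 105 analysed, margin ±0.3, true difference zero and a two-tailed 5% level, the protocol claims 90% power. It treats a larger SD as unlikely and claims 80% power for an SD up to 0.89. No figure is given at 1.03.

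Item 2 (superiority over usual care) takes "a between group mean (SD) difference in AQLQ at 6 months of 0.38 (1.03") from GLAD. The face-to-face comparison is powered "assuming that the common standard deviation is 1.03, when the sample sizes are 105 in the face-to-face breathing retraining and 210" in usual care. The DVD comparison, with 130 per arm, uses the same SD. A second approach in item 2 uses an SD of 0.41 from a within-person MCID; it gives 10 v 20 and 13 v 13 and does not set the trial size.

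Section 8.1, Statistical Analysis, item 1 declares equivalence only if the 95% CI for the 12-month difference lies wholly between -0.3 and +0.3. Section 3, in the opening of Phase 2, describes GLAD as "a 2 armed RCT comparing face-to-face physiotherapist breathing instruction with a control of asthma education (16"). Section 1.1 adds that its control group had the same amount of professional contact time.

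**The concern.** A two-group calculation needs the patient-level SD within an arm. Comparing two breathing programmes may shrink the difference in means, which the protocol already sets to zero. It gives no reason for patients within an arm to differ less from one another. The argument also starts from a usual-care control in GLAD, which sections 1.1 and 3 do not describe.

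A smaller SD lowers the required sample size and raises power, so the cut favours the design. The sensitivity statement stops at 0.89, short of the 1.03 from which the cut was made.

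Section 3 calls the study dual powered, for superiority and for equivalence. If the equivalence arm of that claim is overstated, two programmes with identical effects could well yield an inconclusive interval, and the protocol would not have warned of it. The cost-minimisation step in the health economic section is likewise conditional on this comparison succeeding.

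**Working it through.** **Inputs (protocol section 8.1).** n = 210 and 105; margin 0.3; true difference 0; 95% CI rule; SDs 0.77, 0.89 and 1.03. The stated cut is 1.03 × 0.75 = 0.7725, which gives 0.77.

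**How 1.03 is used.** The superiority figures reproduce if 1.03 is a per-arm SD with a one-sided 5% test:
- 105 v 210: SE = 1.03 × √(1/105 + 1/210) = 0.1231; power = Φ(0.38/0.1231 − 1.645) = 92.5% (stated 92%).
- 130 v 130: SE = 1.03 × √(2/130) = 0.1278; power = Φ(0.38/0.1278 − 1.645) = 90.8% (stated 90%).

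So 1.03 is treated as the spread between patients, the same quantity as the 0.77 in item 1.

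**Reproducing the stated equivalence power.** SE = SD × √(1/210 + 1/105) = SD × 0.11952, giving 0.0920 (SD 0.77), 0.1064 (0.89) and 0.1231 (1.03). Three formulas were tried:
- A: both 95% CI limits inside ±0.3 (the protocol's rule), 2Φ(0.3/SE − 1.96) − 1
- B: one one-sided 2.5% test, Φ(0.3/SE − 1.96)
- C: two one-sided 5% tests (90% CI), 2Φ(0.3/SE − 1.645) − 1

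| SD | Stated | A, normal (exact t) | B, normal | C, exact t |
|---|---|---|---|---|
| 0.77 | 90% | 80.6% (80.3%) | 90.3% | 89.2% |
| 0.89 | 80% | 61.0% (60.6%) | 80.5% | 75.8% |
| 1.03 | none | 36.7% (36.1%) | 68.3% | 56.9% |

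Only B matches both stated figures. B counts one limit of the interval, whereas the decision rule requires both.

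**Separating the two effects.**
- Formula: at SD 0.77, 90% becomes about 80%; at 0.89, 80% becomes about 61%.
- SD: from 0.77 to 1.03, about 80% becomes 36% under the CI rule, or 90% becomes 68% on the calculation that matches the stated figures.

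**What 36% means.** At SD 1.03 the CI half-width is 1.96 × 0.1231 = 0.241. The observed difference must therefore fall within about ±(0.300 − 0.241) = ±0.06. With a true difference of zero, equivalence would be missed about 64% of the time.

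**Size for reference.** Under the CI rule at 2:1, SD 1.03 needs about 374 v 187 analysed for 80% power and 462 v 231 for 90%. With 210 v 105, 80% power holds only up to an SD of about 0.772, and 90% only up to about 0.694.

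**Could baseline adjustment give 0.77?** (0.77/1.03)² = 0.559.
- If 1.03 is the unadjusted SD of a follow-up score, the residual SD is 1.03√(1 − r²). Reaching 0.77 needs r = √(1 − 0.559) ≈ 0.66.
- If 1.03 is the SD of change (equal variances at both times), the factor is √((1 + r)/2). Reaching 0.77 needs r = 2 × 0.559 − 1 ≈ 0.12, and a higher r gives a smaller reduction.

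The protocol does not say which applies.

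**The case against.** The assumption is disclosed, with a rationale and a partial sensitivity range, so nothing is hidden. That stands, but the range ends before the cited value and its power figures do not follow from the decision rule.

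Several stronger readings are tempting, and the document does not support them:
- *The SD explains the whole fall from 90% to 36%.* It does not. Part of the fall is the formula, which is a separate error.
- *The two SDs cannot both hold.* They could if usual care were more variable than the active arms, since each common SD belongs to a different pair. The protocol does not argue this, so the supported statement is that no valid reason is given.
- *1.03 is the only SD available.* Item 2 also cites 0.41, although that value does not set the trial size.
- *The protocol claims 0.77 is a cautious SD.* The word conservative may only mean that a 25% cut is modest. It still misleads, because any cut raises power.
- *Failed equivalence will be taken as a difference.* The analysis plan instead runs a separate ANCOVA, with a difference and 95% CI, to examine superiority of face-to-face.

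Baseline adjustment is the best defence of a smaller SD. The protocol does not invoke it for the sample size. In the equivalence analysis it names ANCOVA only for the step after equivalence is not shown.

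**Conclusion.** The point holds. The protocol gives no valid reason for cutting the SD from 1.03 to 0.77 for the equivalence comparison, and the cut is optimistic. Separately, the stated 90% and 80% are not the power of the declared rule: at those SDs the rule delivers about 80% and 61%. At SD 1.03 it delivers about 36%.

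These figures assume 210 v 105 analysed, a true difference of exactly zero, equal SDs in the two arms, and an unadjusted 95% CI as described in the equivalence analysis. The 36% is conditional on 1.03 being the right SD, which the document cannot settle. The formula discrepancy does not depend on that.

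**What to change.** In section 8.1, Sample Size, item 1:
- Restate equivalence power under the 95% CI rule as about 80% (SD 0.77), 61% (0.89) and 36% (1.03).
- Use 1.03 as the base case unless a smaller SD is justified.
- Delete the word conservative and the wording that treats a higher SD as unlikely.
- Describe the GLAD control as asthma education, in line with sections 1.1 and 3.

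If a smaller SD is to be defended through baseline adjustment, specify the equivalence CI as baseline-adjusted (ANCOVA), state whether 1.03 is the SD of a follow-up score or of change, and apply the same reduction to the superiority calculations.

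No extra patients are required for this. The cost is redrafting and a less favourable stated power; the restatement makes the limitation visible but does not remove it.

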A 2007 UK primary care based RCT (17) demonstrated that breathing retraining and relaxation taught by a physiotherapist in face-to-face sessions significantly reduced respiratory symptoms and improved health-related quality of life in comparison with 'usual care'. The population studied consisted of community treated asthmatics with mild and moderate disease. The contents of the breathing training programme in this study were very similar to those in our proposed study, but only face-to-face instruction was investigated and no economic analysis was made. A Canadian RCT published in 2008 (12) adds further support to breathing training in asthma, also finding significant reductions in asthma symptoms. In this study, a breathing training intervention delivered by physiotherapists in a face-to-face setting was compared to the Butekyo breathing method (also taught in face-to-face sessions by a therapist). Large magnitude but similar improvements from baseline levels of health status and symptoms were seen in both groups.

The most recent and largest RCT was published in 2009 and investigated the effects of a physiotherapist-delivered breathing training intervention of very similar content to that proposed in the face-to face arm of the current trial (16). This study controlled for non-specific 'placebo-like' effect of professional contact and sympathetic attention by giving the control group the same amount of professional contact time (with an experienced respiratory nurse providing asthma education). Significant improvements from baseline were seen in patient-reported asthma outcomes for both groups after 1 month, with trends favouring the breathing training group, and at 6 months a large and significant difference between groups as found in favour of breathing training. Significant improvements were seen between groups in asthma-related quality of life, anxiety and depression and in Nijmegen questionnaire score (measuring

BREATHE Page 13 of 35 Protocol v6 01-08-2014

hyperventilation-related symptoms), and a trend was seen for an improvement in symptomatic asthma control. No effect on airway inflammation or physiology was found. No economic evaluation was made.

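### The only stated reason for cutting the equivalence SD from 1.03 to 0.77 describes the GLAD control as usual care, which the protocol contradicts elsewhere

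*Protocol*

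**What the plan says.** Section 8.1, part 1 (equivalence) starts from GLAD's SD of 1.03 and lowers it by 25% to 0.77. It gives one reason: the planned analysis will "compare two breathing training interventions as opposed to a breathing intervention versus usual care in the GLAD study". With 0.77, a margin of 0.3, a two-tailed 5% level and the assumption "that the expected between group difference in mean AQLQ is zero", it states 90% power for 210 v 105. It adds that power stays at 80% for an SD of up to 0.89. Under the analysis plan in the same section, equivalence is declared only if the 95% CI lies wholly between -0.3 and +0.3.

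Two other sections describe GLAD differently. Section 3 (Phase 2) calls it "a 2 armed RCT comparing face-to-face physiotherapist breathing instruction with a control of asthma education (16", the number being a reference. Section 1.1 describes reference 16 as "giving the control group the same amount of professional contact time (with an experienced respiratory nurse providing asthma education", and says of the purpose: "This study controlled for non-specific 'placebo-like' effect of professional contact and sympathetic attention".

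Section 8.1, part 2, under the heading "For superiority of both the DVD-delivered and the face-to-face programme over 'usual care", sizes superiority "using estimates from the GLAD study, a between group mean (SD) difference in AQLQ at 6 months of 0.38 (1.03" and does not say what the comparator in GLAD was.

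**The concern.** The argument for the smaller SD is a contrast: GLAD set a breathing programme against usual care, whereas the new comparison sets two delivered programmes side by side and should therefore vary less. On the protocol's own account elsewhere, GLAD also compared two delivered programmes with equal professional contact. The contrast as stated does not exist, and no other reason for the reduction is offered.

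The sentence matters because the SD drives the equivalence power. Equivalence with face-to-face is one of the two aims for which section 3 says the trial is powered, and the planned cost-minimisation step rests on the same comparison. The protocol's sensitivity statement stops at an SD of 0.89, short of the 1.03 actually observed, so a reader is never shown the power at the source trial's own value.

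In part 2, using 0.38 under a usual-care heading without naming GLAD's control invites the reader to take it as an effect over usual care.

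**Working it through.** **The descriptions side by side**

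- Section 8.1, part 1: GLAD, breathing intervention against usual care.
- Section 3, Phase 2: GLAD, reference 16, breathing instruction against asthma education.
- Section 1.1: reference 16, breathing training against nurse-led asthma education with the same contact time.

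Only section 3 names GLAD, and only section 1.1 states that contact was matched. Reference 16 links them. The description in section 8.1 cannot stand with the other two.

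**Inputs (section 8.1)**

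Analysed numbers 210 and 105; margin 0.3; true difference 0; 95% CI, so 2.5% in each tail; SD 0.77 (0.75 × 1.03 = 0.7725), 0.89 and 1.03.

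**Formulas**

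SE = SD × √(1/210 + 1/105) = SD × 0.1195.

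Power against one bound ≈ Φ(0.3/SE − 1.96).

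Power for the stated rule, both bounds ≈ 2Φ(0.3/SE − 1.96) − 1.

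The t columns use the non-central t (one bound) or integrate over the sample SD (both bounds).

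| SD | SE | 0.3/SE | One bound, normal | One bound, t | Both bounds, normal | Both bounds, t |
|---|---|---|---|---|---|---|
| 0.77 | 0.0920 | 3.260 | 90.3% | 90.1% | 80.6% | 80.3% |
| 0.89 | 0.1064 | 2.820 | 80.5% | 80.3% | 61.0% | 60.6% |
| 1.03 | 0.1231 | 2.437 | 68.3% | 68.1% | 36.7% | 36.1% |

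The protocol's 90% (SD 0.77) and 80% (SD 0.89) reproduce in the one-bound columns only. Under the stated CI rule they become 80% and 61%. That gap is a separate error and has nothing to do with GLAD's comparator. The part that belongs to this point is the movement down a column. Going from 0.77 to 1.03 takes power from 90% to 68% against one bound, or from 80% to 36% under the stated rule.

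**Superiority (5% one-sided, difference 0.38, SD 1.03, tested against zero)**

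Power ≈ Φ(0.38/SE − 1.645).

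- 105 v 210: SE = 0.1231; 3.087 − 1.645 = 1.442; 92.5% (t: 92.4%). Stated: 92%.
- 130 v 130: SE = 0.1278; 2.974 − 1.645 = 1.329; 90.8% (t: 90.7%). Stated: 90%.
- 210 v 210, the number planned for DVD v usual care: SE = 0.1005; 3.780 − 1.645 = 2.136; 98.4% (t: 98.3%).

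The stated figures reproduce.

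**The case against.** The case on the other side is that this is a slip of wording. Section 3 states the right comparator, so nothing is concealed. Two programmes with similar content might indeed vary less than a breathing programme and an education programme, so 0.77 could be right for a reason the protocol does not give. That possibility stands: the documents do not show 0.77 to be wrong. But the reason actually written is the usual-care contrast, and it is the only one. The superiority calculation also applies 1.03 to the same two arms when each is set against usual care.

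Two stronger readings are tempting, and neither is supported.

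- A reader might infer that the zero-difference assumption fails, because face-to-face includes three contact sessions and the DVD none, while GLAD removed the contact effect. The protocol lists zero openly as an assumption and does not rest it on GLAD. Its rationale hypothesises effects of similar size, and section 1.1 cites video-taught programmes with improved health status as preliminary support. That both GLAD groups had improved at 1 month is an uncontrolled change and does not isolate a contact benefit. Planning equivalence at zero is conventional.
- A reader might infer that superiority is underpowered because 0.38 is not a usual-care effect. Part 2 uses 0.38 as a difference to detect. If contact itself helps, a contact-matched comparison would understate face-to-face against usual care. The mislabel gives no ground for calling superiority underpowered.

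**Conclusion.** The point holds in this form: section 8.1 justifies the 25% reduction in SD by a description of GLAD that sections 1.1 and 3 contradict, and the stated equivalence power is left resting on an unsupported SD. If GLAD's SD of 1.03 applied unreduced, power for 210 v 105 under the stated rule would be about 36% (68% against one bound), compared with about 80% (90%) at 0.77.

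These figures assume a true difference of zero, exactly 210 and 105 analysed, an unadjusted comparison of means, and that GLAD's 6-month SD carries over to 12 months. They show how much depends on the reduction. They do not establish that the trial's power is 36%, since the true SD is not known from the documents. Of the shortfall from 90%, the first 10 points or so (90% to 80% at SD 0.77) come from the separate one-bound error and should not be counted here.

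**What to change.** 1. In section 8.1, part 1, describe GLAD's control as asthma education with matched professional contact, and drop the sentence as a reason for the smaller SD. If 0.77 is kept, give another source or call it an assumption.
2. Restate equivalence power for 210 v 105 under the stated 95% CI rule at a true difference of zero: about 80% at SD 0.77, 61% at 0.89 and 36% at 1.03.
3. In section 8.1, part 2, label 0.38 (SD 1.03) as GLAD's 6-month difference against asthma education. The superiority powers need no change on this account.
4. Optional: show power at a small non-zero face-to-face advantage, with SD 0.77 and the stated rule: 74% at 0.05, 57% at 0.10 and 37% at 0.15. These advantages are assumed values, since the protocol gives none, and the display would not show that zero is wrong.

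The cost is protocol wording and a few restated power figures. It needs no extra patients and no change to the analysis, but the stated equivalence power becomes less favourable.

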#### Health economic evaluation

The resources needed to design and develop the DVD intervention will be recorded during phase 1. During the trial we will also record all resources required to provide the interventions in the DVD and the 'face-to-face' physiotherapy groups. Information will also be collected on all asthma-related healthcare costs for the 1-year follow up period. These will be collected using medical records to collect all asthma related NHS service use (primary and secondary care patient contacts, investigations and prescriptions) with maximum possible use of electronic records, supplemented where necessary by paper records. Respondent questionnaires will be completed at 3 month and 12 month data collection points to quantify time off work/college; and out of pocket expenses. This will constitute a societal perspective to the analysis.

Resources will be costed using appropriate local and national cost data. Total NHS and societal costs will be estimated for each group allowing estimates of the incremental costs of the breathing DVD and 'face-to-face' physiotherapy programmes compared to usual care. Health related quality of life will be assessed using the EuroQol (EQ5D) collected at baseline, 3, 6, and 12- months. These EQ5D scores will be used to generate quality adjusted life years (QALYs). No mortality differences are expected. The superiority analyses will include a cost-utility study (cost per QALY) and cost-effectiveness (cost per significant change in asthma-related health status, i.e. a change of 0.5 in the AQLQ score). If non-inferiority is proven between the face-to-face and DVD interventions, cost minimisation will be carried out. Where appropriate, incremental costeffectiveness ratios (ICERs) and cost-effectiveness acceptability curves (CEACs) will be estimated. Sensitivity analysis will be used to test any major assumptions made in the costing/analysis process. We will check for the extent of missing data at the analysis stage. If considered necessary, we will use appropriate statistical methods (for example multiple imputation) to impute missing data. This will be presented as a sensitivity analysis, i.e. in addition to the complete case analysis.

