#### Statistical Analysis:

#### 1. Analysis plan for equivalence study

Analysis and reporting of the equivalence comparison will follow published guidelines. It is known that full analysis set or ITT may lead to bias (from protocol violators, withdrawals and dropouts) and a resultant increase in type 1 error risk. Therefore, for the equivalence study, an ITT and a per protocol analysis will run simultaneously, neither having supremacy over the other. They should hopefully lead to similar conclusions giving the study a robust interpretation.

A 95% CI will be constructed for the mean difference in 12 month total AQLQ score between the DVD arm and the 'face-to-face' breathing retraining arm. Since the equivalence boundary is set at 0.3, equivalence will be declared if the 95% CI is wholly included between -0.3 and +0.3. If equality is not evident, then ANCOVA will be used to examine whether the 'face-to-face' breathing retraining arm is superior to the DVD arm via examination of the difference (and 95% confidence interval) of 12 month total AQLQ score (and each of the four domain scores) before and after adjustment for baseline AQLQ score and potential covariates such as age, gender, practice, smoking status etc.

BREATHE Page 27 of 35 Protocol v6 01-08-2014

ANCOVA will also be used to analyse the difference (and 95% confidence interval) for the secondary outcome measures (ACQ, lung function, fraction of exhaled nitric oxide, EuroQOL, anxiety and depression score, hyperventilation and patient enablement scores) at 12 months before and after adjustment for baseline values and potential confounders. Since we have data on AQLQ, ACQ and HADS at four time points (baseline, 3, 6 and 12 months) a repeated measures analysis will be used to examine change in each of these outcomes over time. For those secondary outcomes which involve count data (i.e. oral corticosteroid courses, bronchodilator use, asthma related healthcare resource use), Poisson regression analyses with a log link function will be performed to give rate ratios (and their 95% confidence intervals) in the DVD and 'face-to-face' breathing retraining arm both before and after adjustment for potential confounders such as smoking status and sociodemographic factors.

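### The stated 90% power for equivalence (80% at SD 0.89) counts only one of the two limits; the 95% CI rule gives about 80% (61%)

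*Protocol*

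**What the plan says.** The equivalence part of the sample size (protocol section 8.1) states that 210 DVD and 105 face-to-face participants "are required to assess treatment equivalence with 90% power using an equivalence boundary for AQLQ of 0.3". The listed assumptions are "that the expected between group difference in mean AQLQ is zero", a two-tailed 5% level and a "common standard deviation for AQLQ of 0.77 and a lower/upper limit of -0.3/+0.3 for the 95% confidence interval". On the level, the text says that because this is an equivalence study and not a non-inferiority study, "a two-tailed 5% significance level was used in the calculations".

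A fallback follows. If the SD is larger than planned, "we would still have 80% power to declare equivalence between the DVD breathing retraining group and the 'face-to-face' physiotherapy group", provided that the SD does not exceed 0.89.

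The analysis plan for the equivalence study (section 8.1, Statistical Analysis) fixes the decision rule: "equivalence will be declared if the 95% CI is wholly included between -0.3 and +0.3".

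The health economic evaluation in section 7 uses another term for the same comparison: "If non-inferiority is proven between the face-to-face and DVD interventions, cost minimisation will be carried out".

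**The concern.** An interval lies inside ±0.3 only if its lower limit is above -0.3 and its upper limit is below +0.3. With a true difference of zero, the trial can fail on either side with equal probability, so the type II error has to be counted twice. The printed powers look as if it was counted once.

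The equivalence comparison sets the size of the trial. Superiority of the DVD over usual care needs only 130 per arm for 90% power in the protocol's own calculation, whereas equivalence leads to 210 v 105. If its power is overstated, funder and oversight committees have accepted a higher chance of an inconclusive equivalence result than they were told. The fallback at SD 0.89 would also give no real protection. That matters because the planning SD of 0.77 is already 25% below the 1.03 of the earlier trial (1.03 × 0.75 = 0.77).

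**Working it through.** **Inputs** (all from section 8.1): n = 210 (DVD) and 105 (face-to-face); margin 0.3; true difference 0; two-tailed 5%, i.e. 2.5% in each tail, which matches a 95% CI; SD 0.77, and 0.89 for the fallback.

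**Standard error.** k = √(1/210 + 1/105) = 0.1195, and SE = SD × k.
- SD 0.77: SE = 0.0920, and 0.3/SE = 3.260
- SD 0.89: SE = 0.1064, and 0.3/SE = 2.820

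**Step 1: reproduce the printed figures.** For one one-sided 2.5% test against one limit, power = Φ(0.3/SE − 1.960).
- SD 0.77: Φ(1.300) = 90.3% (noncentral t: 90.1%)
- SD 0.89: Φ(0.860) = 80.5% (noncentral t: 80.3%)

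Both printed values come back. The matching sample-size formula gives 104 in the face-to-face arm, against the stated 105.

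**Step 2: power of the stated rule.** Both limits must be cleared, so at zero difference power = 2Φ(0.3/SE − 1.960) − 1.
- SD 0.77: 2 × 0.903 − 1 = 80.6%
- SD 0.89: 2 × 0.805 − 1 = 61.0%

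The exact version uses t critical values on 313 df and integrates over the sampling distribution of the SD. It gives 80.3% and 60.6%. A simulation of 400,000 trials gives 80.5% and 60.7%.

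**Step 3: other readings of the printed pair** (normal approximation, exact in brackets where computed).

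| Calculation | SD 0.77 | SD 0.89 |
|---|---|---|
| Printed | 90% | 80% |
| One one-sided 2.5% test, one limit | 90.3% (90.1%) | 80.5% (80.3%) |
| Two one-sided 5% tests (90% CI) | 89.4% (89.2%) | 76.0% (75.8%) |
| One one-sided 5% test | 94.7% | 88.0% |
| Two one-sided 2.5% tests (95% CI, the stated rule) | 80.6% (80.3%) | 61.0% (60.6%) |

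Only the single-limit 2.5% test reproduces both figures.

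**Step 4: what the design supports.** With 210 v 105 and the 95% CI rule, the largest SD (exact) is 0.694 for 90% power and 0.772 for 80%. The protocol states 0.77 and 0.89. At the earlier trial's SD of 1.03, power would be about 36%.

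**Step 5: sample size for a true 90%.** At SD 0.77 with 2:1 allocation, the face-to-face n = 1.5 × [0.77 × (1.960 + 1.645)/0.3]² = 128.4, so 129 v 258. The exact calculation needs 130 v 260. With 2:2:1 allocation and 10% dropout, 260/0.9 = 289 and 130/0.9 = 145, so 289 + 289 + 145 = 723 recruited, against 585.

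**The case against.** The arithmetic is not in dispute, but several points limit its reach.

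- **A conventional level remains.** At the planning SD the design still has about 80% power. The decision rule is sound, so the error cannot create a false claim of equivalence, and it leaves the superiority powers untouched. All of this stands, and it bounds the harm. It does not make the printed figures right.
- **The 90% could come from two one-sided 5% tests.** Taken alone it could (89.2%). That reading gives 75.8% at SD 0.89, not 80%, and it conflicts with the two-tailed 5% level and the 95% CI rule. Even then, the rule as written has 80% power.
- **A named equivalence program was used.** Its settings are not shown, so how the error arose cannot be known. The single-limit test is a numerical match and not a proven cause. The mismatch does not depend on it.
- **Baseline adjustment could recover power.** If 0.77 is an unadjusted SD and the equivalence interval were adjusted, an assumed baseline correlation of about 0.44 would restore 90% at SD 0.77, and about 0.5 would restore 80% at SD 0.89. The protocol states no adjustment for the equivalence interval, since ANCOVA enters only if equivalence is not shown. The sample-size text claims no such gain. The point limits how well 80% and 61% predict actual power, but it does not support 90% and 80%.
- **The economic trigger is a separate matter.** True: the non-inferiority wording there is an inconsistency of its own and has no effect on the power.

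**Conclusion.** The stated powers are wrong for the stated rule. With 210 v 105, a true difference of zero and the 95% CI required to lie within ±0.3, power is 80.3% at SD 0.77 (stated 90%) and 60.6% at SD 0.89 (stated 80%). The shortfalls are about 10 and 19 percentage points, and the type II error roughly doubles in both cases. The offered cushion on the SD does not exist, because 80% power already runs out at the planning value of 0.77.

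This rests on an unadjusted two-group comparison with 0.77 and 0.89 taken as the common SD, as the protocol describes, and on the full 210 and 105 being analysed. Since the ITT and per-protocol analyses have equal standing, a smaller per-protocol set would have lower power still.

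**What to change.** Correct the equivalence paragraph of section 8.1 to say that 210 v 105 gives about 80% power at SD 0.77 and about 61% at SD 0.89 under the 95% CI rule, and that 80% power holds only up to SD 0.77. The cost is a less favourable stated power. No patients are added and the decision rule stays as it is.

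If the team wants to keep both the rule and 90% power, about 260 v 130 must be analysed, or roughly 723 recruited in place of 585. The synopsis allows extended recruitment only to reach 525 complete data sets, so this would need a separate decision.

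Changing the hypothesis to non-inferiority would make the printed figures correct, but it would alter the design set out in sections 3 and 8.1. It should not be used merely to rescue a power statement. In the same amendment, bring the cost-minimisation trigger in the health economic evaluation into line with the equivalence rule; this is a wording change.
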